7.7. Handling missing data

In the first instance, analysis will be completed on received data only with every effort made to follow-up patients to minimise any potential for bias. In E-MOTIVE, there is the potential for missing outcome data and missing covariate data, which is described below. A planned sensitivity analysis using multiple imputation to allow for missing data is described in section 7.11.

Missing outcome data

Primary outcome

Only blood loss data that is source verified is included in the primary analysis of the primary outcome. There are two reasons that a woman could have missing outcome data, (i.e., missing source verified blood loss data): 1) woman has blood loss data recorded but it is not source verified; and 2) woman has no blood loss data recorded on the case report form.

Secondary clinical outcomes

Secondary clinical outcomes may contain some missing data. Blood loss outcomes (blood loss 2 hours postpartum and 24 hours postpartum) and primary PPH may contain missing data for the same reason as the primary outcome. Other outcomes may contain missing information if the case report form containing outcome data has not been completed fully.

Secondary Implementation outcomes

For all implementation outcomes, the case report form denotes whether a woman received the outcome in question. It is assumed if it was not denoted as a “yes” on the case report form that the woman did not receive the outcome. As such, there is no missing data for the implementation outcomes.

Missing covariate data

All cluster-level data included in (unadjusted) primary analysis models (country, oxytocin quality, cluster size) will be complete and not contain any missing information. Country is known for each participant based on their cluster. The quality of Oxytocin has been measured and evaluated for all clusters. The cluster size will be based on the number of patients in the cluster during the baseline period.

Individual data included in the (adjusted) sensitivity analysis models (age; parity; multiple pregnancy; mode of birth; and birth weight) may contain missing data.

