As agreed in the DMC charter, at the 3rd DMC meeting (after approximately 75% of births), the DMC will be asked to consider whether there is any clear evidence of substantial selection bias. In the unlikely event that substantial selection bias is confidently identified, then the TSC and TMG will consider whether the sensitivity analysis (with PS) will become the primary analysis for all outcomes. Any decision will be documented in the meeting minutes.

Accounting for missing data

The potential for missing outcome data and missing covariate data is discussed in section 7.7. Below, we present multiple imputation methods to deal with missing outcome and individual-level covariate data. We consider this under two assumptions:

- 1) Data missing is missing at random (MAR)
- 2) Data missing is missing not at random (MNAR).

To evaluate the impact of missing data under MAR and MNAR mechanisms, multiple imputation will be used. We will impute the primary outcome (for all women who do not have source-verified primary outcome data) and individual level covariates (for any covariate used in the adjusted analysis).

Missing at Random

We firstly perform multiple imputation using chained equations [18]. The primary outcome and all covariates required for the adjusted analysis with missing data will be included in the imputation process. The following auxiliary variables will be included to aid the imputation process: country; cluster size (above or below median); Oxytocin quality (high or low); time period (baseline or post-randomisation); exposure to E-MOTIVE; previous C-section; gestational age; antepartum haemorrhage; retained placenta; and non-source verified blood loss.

The number of imputations, n , will be equal to the proportion of patients with any missing primary outcome data. To ensure inferences are valid, clustering will be allowed for in the imputation process. This will be done using BLIMP 3.0 which allow a random effect for cluster to be included [19].

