In each imputed dataset, a propensity score is obtained by fitting a multivariable logistic model with potential confounders (age; parity; multiple pregnancy; mode of birth; and birth weight) in the model, and treatment arm as the outcome. In each imputed dataset, the analysis model with PS included in the model as a covariate is fitted and an estimate of the summary measure is obtained. The RR and RD will be obtained in the same manner as for the primary analysis – using marginal standardisation. The summary measure from each of the n imputed datasets is then pooled using Rubin's rules.

Missing Not at Random

An analysis to assess the effect of missing responses for the primary outcome only. This analysis will explore the possibility that missing responses are 'missing not at random' (MNAR) using a tipping point approach.

We firstly perform multiple imputation using chained equations [18]. The primary outcome and all covariates required for the adjusted analysis with missing data will be included in the imputation process. The following auxiliary variables will be included to aid the imputation process: country; cluster size (above or below median); Oxytocin quality (high or low); time period (baseline or post-randomisation); exposure to E-MOTIVE; previous C-section; gestational age; antepartum haemorrhage; retained placenta; and non-source verified blood loss.

The number of imputations, n , will be equal to the proportion of patients with any missing primary outcome data. To ensure inferences are valid, clustering will be allowed for in the imputation process. This will be done using BLIMP 3.0 which allow a random effect for cluster to be included [19].

For the MNAR mechanism, we will assume the prevalence of the primary outcome differs in those patients with a missing outcome compared to those patients with an observed primary outcome. To do this, we will include a parameter in the imputation process that shifts the expected prevalence (of the primary outcome) by a fixed amount. This "*missing parameter*" is a fixed value, and the magnitude and sign of the coefficient determines the strength and direction of the missing not at random process (see below). This parameter is included in each arm separately, to allow the MNAR mechanism to influence one arm at a time.

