Appendix D: Data manipulations

The Trial Statistician will derive all responses from the raw data recorded in the database.

The following variables will be obtained directly from the raw data – where they are recorded in an appropriate form for analysis:

Cluster demographics

- Country (Kenya, Nigeria, South Africa, Tanzania)
- Number of births (total, caesarean, and vaginal) during study from weekly facility forms
- Number of births contributing to the study from pregnancy outcome forms
- Number of staff (Consultant Obstetrician; Medical Doctor; Clinical Officer; Medical Student; Nurse; Midwife; Nurse Midwife; Nurse/Midwifery student; other healthcare professional) – data is collected monthly, and the average number of staff in each category per month will be collated for each cluster

Individual patient demographics

- Previous births (Numerical)

- Previous caesarean section (Yes or No)
- PPH in previous pregnancy (Yes or No)
- Age (Numerical)
- Index birth
- Multiple pregnancy
- Mode of birth (Spontaneous vaginal or forceps or ventouse)
- Birth weight (Numerical)
- Gestational age at birth (Numerical)
- Antepartum haemorrhage (Yes or No)
- Preeclampsia (Yes or No)
- Labour augmented or induced (Yes or No)
- Retained placenta or manual removal of the placenta (Yes or No)

Primary Outcome Components

- Laparotomy for bleeding (Yes or No)
- Maternal mortality for bleeding (Yes or No)

Secondary/Exploratory Clinical Outcomes

- Laparotomy (Yes or No)
- Laparotomy with compression sutures (Yes or No)
- Laparotomy with arterial ligation (Yes or No)
- Hysterectomy (Yes or No)
- Hysterectomy for bleeding (Yes or No)
- All cause maternal mortality (Yes or No)
- All cause neonatal mortality (Yes or No)
- Non-pneumatic anti-shock garment (NASG) (Yes or No)
- Uterine balloon tamponade (Yes or No)
- Blood transfusion (Yes or No)
- Blood transfusion for bleeding (Yes or No)
- ICU admissions (Yes or No)
- Transfer to higher level cluster (Yes or No)

Secondary/Exploratory Implementation Outcomes

- PPH detection (Yes or No)
- Uterine massage (Yes or No)
- Oxytocin use (Yes or No)
- Misoprostol use (Yes or No)
- Tranexamic acid use (Yes or No)
- Intravenous fluids use (Yes or No)
- Examination of the genital tract (Yes or No)
- Women receiving any treatment uterotonic (Yes or No)
- Women requiring additional treatment interventions (Yes or No)

The following variables will be derived for analysis from the dataset. Details on how they will be derived is presented.

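### The imputation models in SAP 7.11 omit the recorded signs of bleeding, so for women with no blood loss recorded the missing-at-random analysis largely repeats the complete-case result

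*SAP*

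**What the plan says.** SAP 7.7 restricts the primary analysis to source-verified blood loss and gives two reasons for a missing outcome. Either a loss was recorded but not verified, or the "woman has no blood loss data recorded on the case report form".

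SAP 7.11 (Missing at Random) then states: "The primary outcome and all covariates required for the adjusted analysis with missing data will be included in the imputation process". Those covariates are age, parity, multiple pregnancy, mode of birth and birth weight. The auxiliaries are country, cluster size, oxytocin quality, period, exposure, and "previous C-section; gestational age; antepartum haemorrhage; retained placenta; and non-source verified blood loss". The Missing Not at Random part repeats the same list, adds a fixed shift in prevalence, and applies it to exposed or unexposed women one group at a time.

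SAP Appendix D shows that signs of bleeding are held for analysis: "PPH detection (Yes or No"), "Tranexamic acid use (Yes or No"), other treatments, additional interventions, balloon tamponade, transfusion for bleeding, and loss between 2 and 24 hours. On diagnosis and treatment, SAP 7.7 counts anything not marked yes as not received and concludes: "As such, there is no missing data for the implementation outcomes".

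**The concern.** The two kinds of missing outcome need different information. Where a loss was recorded but not verified, the recorded value is in the imputation model and largely settles the imputed outcome. Where no loss was recorded, that auxiliary is empty too. What remains is design factors, general obstetric covariates, antepartum haemorrhage and retained placenta. None of these says directly whether the woman bled heavily, although the database does.

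It is plausible, though the documents do not show it, that a drape goes unweighed more often when a woman is bleeding and staff are busy. Training, feedback and drape type differ by arm, so this need not be equal between arms. If missingness follows the bleeding signs, the data are missing at random given those signs but not given the SAP's list. The imputed and complete-case estimates would then agree because they share the same gap, and a reader could take the agreement as evidence that missing data did no harm.

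**Working it through.** **Plan figures.** The plan gives no figure for the share with no recorded loss; Protocol 11.2 only expects missing data to be minimal. The effect used is the one in the Protocol summary, 4% to 3%: 3/4 = 0.750, the stated 25% reduction.

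**Inputs taken as proxies**

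| Input | Usual care | E-MOTIVE | Source |
|---|---|---|---|
| True risk | 4% | 3% | Protocol summary |
| Sign recorded, outcome present | 70% | 90% | Protocol 1.1 (68/96 treated at 1000–1100 ml); Protocol Appendix A (target 90%) |
| Sign recorded, outcome absent | 2.5% | 5% | Protocol 1.1 (Tanzanian detection rate); assumed |

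Further assumptions: no loss is recorded for 5% of women without a sign (range 1–10%) and for three times that share with a sign. Retained placenta or antepartum haemorrhage affects 3% and carries a risk ratio of 4. Clustering and the baseline period are ignored, because the question is bias.

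**Usual care, 5% and 15% missing**

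- Women with a sign: 0.04×0.70 + 0.96×0.025 = 0.052.
- Missing: 0.052×0.15 + 0.948×0.05 = 0.0552.
- Events among the missing: 0.028×0.15 + 0.012×0.05 = 0.0048.
- True risk in the missing: 0.0048/0.0552 = 8.7%.
- Observed risk: (0.04 − 0.0048)/(1 − 0.0552) = 3.73%.
- Imputed with the SAP list: observed risk is 13.8% in the stratum with retained placenta or antepartum haemorrhage and 3.42% otherwise. That stratum is 3.4% of the missing, so 0.034×13.8 + 0.966×3.42 = 3.77%.
- Imputed with the sign added: 8.7%.

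**E-MOTIVE, same steps**

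- Women with a sign: 0.0755. Missing: 0.05755. Events among the missing: 0.0042.
- True risk in the missing 7.3%; observed 2.74%; SAP list 2.77%; with the sign 7.3%.

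**Risk ratios**

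If the mechanism acts only in usual care, the SAP-imputed control risk is 0.0352 + 0.0552×0.0377 = 0.0373, and 0.03/0.0373 = 0.805 (complete case 0.0300/0.0373 = 0.805). If it acts only in E-MOTIVE, the risk is 0.0258 + 0.05755×0.0277 = 0.0274, and 0.0274/0.04 = 0.685 (complete case 0.684).

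| Missing if no sign | SAP list, usual care only | SAP list, E-MOTIVE only | SAP list, both arms | Signs added |
|---|---|---|---|---|
| 1% | 0.760 | 0.738 | 0.747 | 0.750 |
| 5% | 0.805 | 0.685 | 0.735 | 0.750 |
| 10% | 0.877 | 0.611 | 0.714 | 0.750 |

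The SAP-list estimate stayed within 0.002 of the complete-case one in every scenario run. With a much stronger listed predictor (5% prevalence, risk ratio 10), the imputed usual-care risk rose only to 4.1%.

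**Missingness driven by the outcome itself (15% against 5%)**

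- Both arms alike: observed risks are 0.034/0.946 = 3.59% and 0.0255/0.947 = 2.69%, a ratio of 0.749. Adding signs gives 0.745.
- Usual care only: 0.834 with the SAP list, 0.803 with signs.
- E-MOTIVE only: 0.674 with the SAP list, 0.696 with signs.

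**Blanks read as 'no'.** If the form is incomplete and every sign reads as absent, the usual-care women would be imputed at 0.012/0.948 = 1.3%, below the observed 3.73%.

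**The case against.** Four points on the other side carry weight.

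1. A reader might infer that every woman without verified loss is imputed at average risk. The documents do not support this, because a recorded but unverified loss is already an auxiliary. For example, take a true risk of 3.6% with verified loss missing in 20% of cases and 10% of others. Observed risk is 0.0288/0.8964 = 3.21%, or 11% too low. Suppose an unverified weight settles the outcome. If 50%, 75% or 90% of the missing women have such a weight, the risk after imputation is only 5.1%, 2.5% or 1.0% too low. The 11% applies only if none of them has a weight. An unphotographed drape belongs to the group that is already covered.

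2. A reader might also infer that the plan has no answer to outcome-related missingness. It has the tipping-point analysis, which shifts prevalence among the missing in exposed and unexposed women separately. That stands as a probe. But it uses the same base model, holds the unshifted group at the observed prevalence, states no range of shifts, and ties them to no recorded sign.

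3. Extent and direction are assumed. No passage shows that unrecorded loss follows severity. Equal outcome-dependent missingness in both arms barely moves the risk ratio.

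4. The signs are imperfect. Blanks are coded 'no', visual loss after two hours is recorded only when it is excessive (SAP 4.5), and transfusion and tamponade may themselves be missing. This shapes the fix; it is no reason to leave the signs out.

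**Conclusion.** The point holds for women with no blood loss recorded, in the missing-at-random analysis and the base model of the tipping-point analysis. For them the listed variables give an imputed risk near the observed average, apart from small shifts for retained placenta and antepartum haemorrhage. Agreement with the complete-case result is therefore weak evidence about bleeding-related missingness in this group.

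The documents do not support saying that the primary estimate is biased, or that the bias has a known size or sign. The figures above rest on assumed missingness, proxy sign rates and, for the larger shifts, a mechanism confined to one arm. At 1% unrecorded the risk ratio moves by about 0.01, and at 10% by about 0.13 or 0.14. This is a worthwhile improvement to a sensitivity analysis, not a fault in the primary analysis.

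**What to change.** In SAP 7.11, in both imputation models:

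- Add attendant diagnosis of PPH, bundle components given, transfusion for bleeding, tamponade, and visual loss from 2 to 24 hours (coded as none recorded, or the amount).
- Enter these with exposure interactions, or fit separate models by exposure, because the intervention is meant to change detection and treatment and so what a sign implies.
- Where the form is incomplete, treat blank signs as missing in the imputation, not as 'no'.
- Tabulate the signs by arm and by type of missingness (unverified, or not recorded), and use that table to prespecify the range of tipping-point shifts.

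The cost is SAP wording, one extra table and a larger imputation model; no new data are needed. If missingness depends on the outcome beyond what the signs capture, correction is only partial (for example 0.834 to 0.803 against a true 0.750), so the tipping-point analysis should stay.

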Every attempt will be made to collect routine clinical details on all women giving birth vaginally in the facilities using an efficient and pragmatic approach; it is thus anticipated that missing data will be minimal. Women with missing primary outcome data will not be included in the primary analysis in the first instance. This presents a risk of bias, and sensitivity analyses will be undertaken to assess the possible impact of the risk. In brief, this may include simulating missing responses using a multiple imputation approach. Full details will be included in the Statistical Analysis Plan.

Source-verified Data

Analyses of outcomes with blood loss data will only include blood loss that has been source-verified. Blood loss measured using the blood collection drape, which is source-verified will have a corresponding photograph, which is uploaded to a secure portal, of the drape on the E-MOTIVE digital weighing scale displaying the drape weight. The photograph should also display the drape weight documented on the E-MOTIVE stickers before being placed in the patient notes. The drape weight value entered on to the E-MOTIVE REDCap database is verified against the drape weight in the photograph and the photograph is linked to the patient record on the database using the E-MOTIVE patient I.D number.

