6.1. Cluster Inclusion Criteria

Health facilities (clusters) are eligible for inclusion if they have 1000 to 5000 births a year and provide comprehensive obstetric care with ability to perform surgery for PPH. Clusters are selected based on being administratively and geographically distinct from each other. Pre-existing implementation of early detection or bundled approach for PPH management are exclusion criteria.

The cluster start date for inclusion in the study, is the date in which $\geq 80\%$ of their patients have source data verification.

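### The number of imputations is set equal to the proportion missing, with no unit, rounding or minimum, so at about 1% missing or less the prescribed pooling cannot be done

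*SAP*

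**What the plan says.** SAP 7.11 plans two imputation analyses, one assuming data missing at random (MAR) and one assuming data missing not at random (MNAR, the tipping-point analysis). In the MAR text the number of imputations "will be equal to the proportion of patients with any missing primary outcome data", and the MNAR text repeats the sentence. Neither gives a unit, a rounding rule or a minimum. In both, "The summary measure from each of the n imputed datasets is then pooled using" Rubin's rules.

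The imputation step covers the primary outcome, for every woman without source-verified outcome data, and the individual-level covariates of the adjusted analysis. SAP 7.7 says those covariates (age, parity, multiple pregnancy, mode of birth, birth weight) may be incomplete. It also counts as missing the case where a "woman has blood loss data recorded but it is not source verified".

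On how much will be missing, Protocol 11.2 says only that "it is thus anticipated that missing data will be minimal". The one numerical reference point is SAP 6.1: a cluster's start date is when at least 80% "of their patients have source data verification".

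Imputation does not enter the primary analysis. SAP 7.7 states: "In the first instance, analysis will be completed on received data only".

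**The concern.** A proportion lies between 0 and 1, so the rule cannot be carried out as written. The likely intention is one imputation per percentage point missing, but the SAP does not say so. On that reading the rule still has no lower limit. If few outcomes are missing it can give one imputation or none, and the pooling that the SAP prescribes is then undefined.

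The rule also counts only missing outcomes, although covariates are imputed in the same step. A data set with few missing outcomes and many missing birth weights would get few imputations.

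What is at stake is whether the missing-data sensitivity analyses can be run as specified and reproduced. The tipping-point analysis is the most exposed. It reads off the shift at which a confidence limit crosses one, and that limit carries simulation error at every shift value tried.

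**Working it through.** The SAP states no number of imputations and no percentage missing, so there is no figure of its own to reproduce. The percentages below are assumptions. Counts of women use the planned total, 80 × 192 × 14 = 215,040 (SAP 4.7).

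**Step 1: what the rule gives.** Let p be the proportion missing. Literally, n = p; at 2% missing, n = 0.02. On the percentage reading, n = 100p.

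**Step 2: when pooling works.** With m imputations, Rubin's rules use T = W + (1 + 1/m)B. W is the within-imputation variance and B the between-imputation variance, with divisor m − 1. At m = 1 the divisor is 0 and B does not exist.

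**Step 3: simulation error when m is 2 or more.** Let g be the fraction of missing information.
- The Monte Carlo error of the pooled estimate, relative to its standard error, is √(g/m).
- The reference distribution is t with (m − 1)(1 + 1/r)² degrees of freedom, where r = (1 + 1/m)B/W.
- The spread of the 95% CI half-width (relative to its value without Monte Carlo error) and the coverage come from 200,000 simulated replicates, with W = 1 − g treated as known and B drawn as g × χ²(m − 1)/(m − 1).

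The table takes g = p.

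| Missing (assumed) | Women of 215,040 | n, nearest integer | Monte Carlo error / SE | Half-width, 95% range | Coverage |
|---|---|---|---|---|---|
| 0.3% | 645 | 0 (1 if rounded up) | not computable | not computable | not computable |
| 1% | 2,150 | 1 | not computable | not computable | not computable |
| 2% | 4,301 | 2 | √(0.02/2) = 0.100 | 0.990 to 1.086 | 0.9500 |
| 3% | 6,451 | 3 | √(0.03/3) = 0.100 | 0.985 to 1.068 | 0.9502 |
| 5% | 10,752 | 5 | 0.100 | 0.978 to 1.064 | 0.9494 |
| 10% | 21,504 | 10 | 0.100 | 0.966 to 1.070 | 0.9498 |
| 20% | 43,008 | 20 | 0.100 | 0.949 to 1.085 | 0.9495 |

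**Step 4: sensitivity to g.** If g is twice the missing share, then at 2% missing and n = 2 the Monte Carlo error is √(0.04/2) = 0.141 of the SE. The half-width range is 0.980 to 1.208 and coverage is 0.9503.

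**Step 5: effect of a floor.** At g = 2% with 20 imputations, the Monte Carlo error is √(0.02/20) = 0.032 of the SE, the half-width range is 0.995 to 1.008 and coverage is 0.9497.

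**Step 6: covariates.** For illustration, assume 1% of outcomes and 10% of birth weights are missing. The rule gives n = 1, although at least 10% of women have an imputed value. Individual covariates enter the MAR analysis model through the propensity score. The MNAR model contains only exposure, period and cluster-level covariates, and SAP 7.7 says the cluster-level data are complete.

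**The case against.** The strongest defence is that one imputation per percentage point is a sensible rule and that the word proportion is a slip. The table supports much of this. With g = p, √(p/(100p)) = 0.1 at every level, so the rule holds Monte Carlo error at a constant 10% of the SE and gives few imputations only where little information is missing. An analyst who arrived at n = 1 would notice, and SAP section 1 allows justified deviations. All of that stands. It does not supply the missing unit, rounding rule and minimum. It also leaves the rule tied to outcome missingness alone, when covariates are imputed too.

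A reader might infer more than the documents support:

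- **That the trial expects only 1% or 2% missing.** The protocol's expectation of minimal missing data has no figure attached. SAP 7.7 counts unverified blood loss as missing, and the 80% verification criterion is compatible with up to 20% missing, hence n up to about 20. That criterion fixes a start date and is not a forecast, so it does not settle the matter either way.
- **That inference from two imputations is invalid.** At n = 2, B is badly estimated (95% range 0.001 to 5.0 times its true value), but it is a small part of T. At g = 2%, r = 1.5 × 0.02/0.98 = 0.031, which at the expected B gives about 1,100 degrees of freedom. The n − 1 = 1 degree of freedom belongs to B and not to the pooled interval. Relative efficiency is 1/(1 + 0.02/2) = 0.990.

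**Conclusion.** The point holds as a specification error of small consequence. As written the rule gives no usable n. On the percentage reading it fails outright only at about 1% missing or less. At 2% to 3% the cost is avoidable variation between runs, including in where the tipping point falls, with coverage essentially preserved. Ignoring covariates matters for the MAR propensity-score analysis but not for the MNAR analysis model.

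The size depends on the share missing, which the documents do not give, and on the assumption that the fraction of missing information is equal to that share or twice it. It could be higher if missingness is concentrated in some clusters or if covariates are also missing. The result of the primary analysis does not depend on n.

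**What to change.** In both the MAR and MNAR parts of SAP 7.11, define n as the larger of a pre-specified minimum and 100 times the proportion of women with any imputed variable missing, rounded up. A minimum of 20 is a reasonable example; the documents do not dictate that figure. The SAP already uses one n throughout the tipping-point analysis, so the only addition there is to use the same random seed at every shift value. If the analyses have already been run, report the n actually used in the Appendix A deviations table.

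The cost is computing time. At 2% missing, a floor of 20 means 20/2 = 10 times as many imputed data sets and model fits at each shift value. If 20% or more of women have an imputed value missing, the floor adds nothing to the percentage rule.
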